7.3.7 Efficacy Analysis

7.3.7.1 Analyses for Primary Outcome

The primary outcome is the diagnostic accuracy of ds-MCE for discrimination of patients with EGV using sensitivity and specificity, along with the corresponding 95% CIs estimated using the Wilson's method¹⁶. Sensitivity and specificity will be compared with 85% using one-sample exact test. The accuracy, and positive and negative predictive values (PPV and NPV) will be calculated as other measures simultaneously, along with the corresponding 95% CIs estimated using the Wilson's method.

- True Positive (a): Both ds-MCE diagnosis and EGD results determine the presence of esophageal or gastric varices, and the location (esophagus or stomach) is consistent.
- False Negative (c): ds-MCE diagnosis determines no cases of esophageal or gastric varices, while EGD results determine the presence of esophageal or gastric varices.
- True Negative (d): Both ds-MCE diagnosis and EGD results determine the absence of esophageal or gastric varices.
- False Positive (b₁): ds-MCE diagnosis and EGD results both determine the presence of esophageal or gastric varices, but the locations (esophagus or stomach) are inconsistent.
- False Positive (b₂): ds-MCE diagnosis determines the presence of esophageal or

gastric varices, while EGD results determine the absence of esophageal or gastric varices.

Table1. Four-grid table for ds-MCE and EGD assessment results

ds-MCE	EGD		Non-varices
	Varices	Inconsistent location in the stomach or esophagus	
Varices	a	b ₁	b ₂
Non-varices	c		d

$$\text{Sensitivity (SE)} = a/(a+b_1+c) \times 100\%$$

$$\text{Specificity (SP)} = d/(b_2+d) \times 100\%$$

$$\text{Accuracy} = (a+d)/(a+b_1+b_2+c+d) \times 100\%$$

$$\text{PPV} = a/(a+b_1+b_2) \times 100\%;$$

$$\text{NPV} = d/(c+d) \times 100\%;$$

Sensitivity Analyses for the Primary Outcome

No sensitivity analysis will be conducted for this study.

7.3.7.2 Analyses for Secondary Outcomes

The training cohort and validation cohort will be divided based on centers, in the order of the first patient in (FPI). Centers with earlier FPI date will be allocated to the training cohort (whose sample size should meet approximately 2/3 of the total sample size), and the remaining centers with later FPI date will be allocated to the validation cohort.

(1) Optimal threshold based on the Training Cohort

The optimal esophageal luminal circumference percentage threshold will be chosen with the Youden Index¹⁷. The Youden Index, defined as [(sensitivity + specificity) - 1], will be calculated to determine the ds-MCE optimal luminal circumference percentage threshold derived from the training cohort that resulted in the best combination of specificity and sensitivity for distinguishing large EV, using the results of EGD as the reference standard. When the optimal threshold has decimals, its integer portion will be set as the modified optimal threshold for internal and external validation (for the ease of clinical application and ensuring sensitivity). Based on the training cohort, the modified optimal threshold is internally validated with bootstrap method, with 1000 replicates.

(2) The diagnostic accuracy of high-risk EV will be assessed on the basis of the modified optimal threshold above in the validation cohort using accuracy, sensitivity, specificity, PPV and NPV, corresponding 95% CIs calculated using the Wilson's method.

(3) The diagnostic accuracy of high-risk EGV will be assessed on the basis of the modified optimal threshold above in the validation cohort using accuracy, sensitivity, specificity, PPV and NPV, corresponding 95% CIs calculated using the Wilson's method.

(4) The diagnostic accuracy of large EV will be assessed on the basis of the modified optimal threshold above in the validation cohort using accuracy, sensitivity, specificity, PPV and NPV, corresponding 95% CIs calculated using the Wilson's method.

(5) The diagnostic accuracy of ds-MCE in detection of EV compared with the EGD will be assessed using accuracy, sensitivity, specificity, PPV and NPV, corresponding 95% CIs calculated using the Wilson's method.

(6) The diagnostic accuracy of ds-MCE in detection of red signs of EV compared with the EGD will be assessed using accuracy, sensitivity, specificity, PPV and NPV, corresponding 95% CIs calculated using the Wilson's method.

(7) The diagnostic accuracy of ds-MCE in detection of gastric varices (GV) compared with the EGD will be assessed using accuracy, sensitivity, specificity, PPV and NPV, corresponding 95% CIs calculated using the Wilson's method.

(8) The diagnostic accuracy of ds-MCE in detection of cardiofundal GV compared with the EGD will be assessed using accuracy, sensitivity, specificity, PPV and NPV, corresponding 95% CIs calculated using the Wilson's method.

(9) The diagnostic accuracy of ds-MCE in detection of portal hypertensive gastropathy (PHG) compared with the EGD will be assessed using accuracy, sensitivity, specificity, PPV and NPV, corresponding 95% CIs calculated using the Wilson's method.

(10) The incidence of PHE in small bowel under ds-MCE will be described using the methodology described in Section 7.3.1.

(11) The examination times of ds-MCE and EGD procedures will be described using the methodology described in Section 7.3.1.

(12) The patient satisfaction score of ds-MCE and EGD procedures will be described using the methodology described in Section 7.3.1.

7.3.8 Subgroup analysis

To determine whether the accuracy is consistent across subgroups, the estimate of the between-group accuracy for EGV, high-risk EV based on the modified optimal threshold value, high-risk EGV based on the modified optimal threshold value will be estimated within each category of the following classification variables:

Cirrhosis stage (compensated phase, decompensated phase);

Indication for endoscopy (screening, surveillance).

7.3.9 Safety Analyses

All adverse events (AE) and serious adverse events (SAE) during the study will be listed. The AE verbatim descriptions collected from the Case Report Form (CRF) will undergo classification into standardized medical terminology using the Medical Dictionary for Regulatory Activities (MedDRA). Adverse events will be coded to the most appropriate MedDRA lower level term (LLT) that closely matches the verbatim term. The associated MedDRA preferred term (PT) and primary system organ class (SOC) will also be recorded in the database.

Summary tables will only include those adverse events that considered related to trial procedure. However, subject data listings will include all adverse events, regardless of whether or not considered related to trial procedure. This approach ensures that adverse events considered related to trial procedure are appropriately captured and analyzed, while all adverse events are documented for comprehensive reporting and analysis.

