7.1 Adverse Events (AE)

Adverse events are defined as any undesirable experience occurring to a subject during the study, whether or not considered related to trial procedure. As far as possible, each AE should be evaluated to determine the severity grade (mild, moderate, severe); its relationship to the study procedure; its duration (start and end dates or if continuing at final exam); action taken (no action taken; hospitalization); whether it constitutes a serious adverse event (SAE). All adverse events reported spontaneously by the subject or observed by the investigator or his staff will be recorded and documented on the designated CRF.

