9.4.9 Safety Analyses

All adverse events and serious adverse events will be listed.

10 Ethical considerations

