4.2.2 Other secondary objectives

- To estimate the diagnostic accuracy of ds-MCE in identifying high-risk EGV, using the detection by EGD as the reference.
- To estimate the diagnostic accuracy of ds-MCE in identifying EV, using the detection by EGD as the reference.
- To estimate the diagnostic accuracy of ds-MCE in identifying large EV, using the

detection by EGD as the reference.

- To estimate the diagnostic accuracy of ds-MCE in identifying red signs of EV, using the detection by EGD as the reference.
- To estimate the diagnostic accuracy of ds-MCE in identifying GV, using the detection by EGD as the reference.
- To estimate the diagnostic accuracy of ds-MCE in identifying cardiofundal GV, using the detection by EGD as the reference.
- To estimate the diagnostic accuracy of ds-MCE in identifying PHG, using the detection by EGD as the reference.
- To assess the incidence of PHE in small bowel under ds-MCE.
- To evaluate the examination time of ds-MCE and EGD procedures.
- To assess the patient satisfaction score of the ds-MCE and EGD procedures.
- Safety evaluation: to record the adverse events occurring during the study.

5. Design

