6.2 Safety outcomes

Safety outcomes in this study will be assessed based on adverse event reporting. All adverse events that occur during the course of the study will be diligently recorded and documented.

7. Statistical Considerations

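### Adverse event tables are limited to events judged procedure-related, so no all-cause rate of adverse events, serious adverse events or deaths is planned

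*SAP*

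**What the plan says.** SAP 7.3.9 sets the rule for reporting: "Summary tables will only include those adverse events that considered related to trial procedure". It continues that "subject data listings will include all adverse events, regardless of whether or not considered related to trial procedure". All events are coded in MedDRA: "The associated MedDRA preferred term (PT) and primary system organ class (SOC) will also be recorded in the database".

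Protocol 9.4.9 is shorter: "All adverse events and serious adverse events will be listed". It plans no table.

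The definition of an adverse event in Protocol 7.1 covers events "whether or not considered related to trial procedure". The SAP's objective (4.2.2) is "Safety evaluation: to record the adverse events occurring during the study", and its safety outcome (6.2) adds that "All adverse events that occur during the course of the study will be diligently recorded and documented". On attribution, Protocol 7.1 says: "As far as possible, each AE should be evaluated to determine the severity grade (mild, moderate, severe); its relationship to the study procedure". SAP 7.3.9.1 repeats this for serious adverse events. Neither document gives criteria or a scale for the judgement.

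**The concern.** Adverse events are defined and collected whatever their cause, but only those attributed to the procedure are counted in a table. Any count or percentage in the safety results then depends on attribution.

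Attribution is difficult here. Protocol 4.2 names variceal bleeding as a possible consequence of ds-MCE and bleeding as a complication of EGD, while Protocol 1 describes variceal hemorrhage as a consequence of the disease itself. A bleed during an examination is comparatively easy to attribute; one in the following days is harder. With a single arm there is no comparator against which to check the attributions.

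Safety is a listed secondary outcome of a device study. If bleeds or deaths are put down to cirrhosis, or if a reader takes the related-only table for the overall rate, harm is understated.

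**Working it through.** The plan states no adverse event rate, so there is no figure to reproduce. The check has two parts.

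**1. Does any other provision supply an all-cause rate?**

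- *SAP 7.3.1* calls for frequencies and percentages of categorical variables. It is generic and does not mention adverse events. SAP 7.3.7.2 refers enteropathy incidence, examination times and satisfaction back to 7.3.1; the safety section makes no such reference. The specific restriction in 7.3.9 governs.
- *SAP 7.3.6* has broad wording about summarising all variables, but it belongs to the baseline section.
- *SAP 7.3.5* tabulates early discontinuation by reason. A death or bleed could appear there only if it ended participation.
- *SAP 7.2* counts the safety set, which gives a denominator but no numerator.
- *SAP 7.3.9.1 and Protocol 7.2* require prompt reporting of death from any cause to the sponsor. This is a reporting duty, not an analysis.
- *SAP 7.3.9.3 and Protocol 7.4* have the sponsor and the data safety monitoring board review all events. This is monitoring and yields no planned table.
- *SAP 7.3.3* excludes imputation for safety outcomes. Read literally, an event whose relatedness was never assessed is not one considered related, and so enters no table.

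None of these supplies an all-cause rate.

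**2. What is the scale?**

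Inputs: 591 planned patients and 3% dropout (SAP 5.3; Protocol 9.2). The size of the safety set is not given and is assumed.

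Let N be the safety-set size, R the number of patients with at least one related event, and U the number whose events are all judged unrelated.

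- All-cause proportion = (R + U)/N
- Tabulated proportion = R/N
- Gap = U/N

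The same holds for serious adverse events and for deaths, each with its own R and U.

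Effect of each patient in U:

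- N = 591: 1/591 = 0.00169, or 0.169 percentage points.
- N = 591 × 0.97 = 573: 1/573 = 0.00175, or 0.175 percentage points.

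U cannot be derived from the documents, so the total gap is unknown.

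An all-cause rate would be informative at this sample size. With purely assumed counts out of 591, the exact (Clopper-Pearson) two-sided 95% interval for 0 events has an upper limit of 0.62%; for 6 events (1.0%) it runs from 0.4% to 2.2%.

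**The case against.** The strongest reply is that the plan does what it says it will do. The objective is to record adverse events and the outcome is that they are recorded and documented; no rate, hypothesis or threshold is promised. The SAP states its restriction openly, and it adds a table to the protocol's listings without contradicting them. Every event is listed and coded, so an all-cause count can be made from the listings at any time.

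The exposure window is also short: participation lasts about two days, with a contact two weeks after ds-MCE, and patients with active gastrointestinal bleeding or life-threatening conditions are excluded. Relatedness is reassessed during follow-up (Protocol 7.3; SAP 7.3.9.2) and can draw on hospital reports. Finally, without a comparator, an all-cause rate in cirrhosis mixes disease, capsule and EGD.

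Most of this stands, but it limits the size of the problem and does not remove it. The documents do not conflict and no data are lost; what is missing is a planned tabulation. The short window reduces the room for the two rates to diverge. Reassessment helps, but still without stated criteria. That an all-cause rate mixes causes is a reason to show both columns; showing only the related one leaves the reader dependent on a judgement that cannot be checked from the tables. It is also fair that 573 is not a true bound: the dropout allowance was made for the sample size, and a patient who drops out after ds-MCE would probably stay in the safety set.

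**Conclusion.** The concern holds. If the plan is followed exactly, no all-cause count or percentage of adverse events, serious adverse events or deaths will be produced, and every tabulated safety result will depend on the relatedness judgement. Related serious events and related deaths would still enter the tables as adverse events; the all-cause figures are what is missing.

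The size of any understatement is unknown. The per-patient step shows scale only and rests on the assumed safety-set size. The sensitivity and specificity analyses are untouched. This should be changed because safety is a stated outcome and the correction is cheap, but it does not threaten the main conclusion.

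**What to change.** Keep the related-event table. Add, on the safety analysis set, the number and percentage of patients, and the number of events, for any adverse event, any serious adverse event and death from any cause, by MedDRA system organ class and preferred term, with the procedure-related subset in a second column. The restricting sentence in SAP 7.3.9 could become: *Summary tables on the safety analysis set will show all adverse events, all serious adverse events and all deaths whatever their cause, with the procedure-related subset in a second column.* Events with no relatedness assessment would then be counted in the first column.

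The cost is a few more tables. Protocol 7.1 already requires all events on the CRF and SAP 7.3.9 already requires their coding, so no new data are needed. The displayed rate will be higher and will include events of the underlying disease; the second column lets readers separate the two.

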7.3.9.1 Serious Adverse Events (SAE)

A Serious Adverse Event is any unfavorable event within the study timeframe fulfilling at least one of the following criteria:

- results in death;
- life-threatening (at the time of the event);
- inpatient hospitalization required or prolonged;
- event that results in persistent or significant disability/incapacity;
- medically important event or event that requires a medical or surgical intervention to prevent one of the above health implications.

Any other important medical event that did not result in any of the outcomes listed above due to interventions but could have been based upon appropriate medical judgment. An elective hospital admission will not be considered as a serious adverse

event.

As far as possible, each SAE should be evaluated to determine the severity grade (mild, moderate, severe); its relationship to the study procedure; its duration (start and end dates or if continuing at final exam); action taken (no action taken; hospitalization).

Serious adverse events will be immediately, after coming to notice of the investigator, reported to the trial coordinator, who is 24/7 available. The investigator will report the following SAEs occurring in the study period to the sponsor without undue delay of obtaining knowledge of the events: death from any cause; esophagogastric variceal hemorrhage during ds-MCE examination; acute esophagogastric variceal hemorrhage during EGD examination; acute esophagogastric variceal hemorrhage during ds-MCE examination. The investigator should report to the sponsor and ethics committee (EC) within 24 hours of SAEs. SAEs need to be documented additionally on a separate SAE form.

7.3.9.2 Follow-up of Adverse Events

All AEs will be followed until they have abated, or until a stable situation has been reached. Depending on the event, follow up may require additional tests or medical procedures as indicated, and/or referral to the general physician or a medical specialist. Assessment should be made at each visit (or more frequently, if necessary) of any changes in severity, the suspected relationship to the study, the interventions required to treat it and the outcome. For a follow-up report, the investigator may be required to collect further information for a detailed description and a final evaluation of the case, including copies of hospital reports, autopsy reports, or other relevant documents.

SAEs need to be reported till the end of the study in China, as defined in the protocol.

